### **3.0 OBJECTIVES**

The primary endpoints of this study are:

1. Repeatability of cutting guide position on the distal femur and proximal tibia assessed by repeated measures using computer navigation system for total knee replacement, assessed intra-operatively (Group A).
2. Radiographic implant location, consisting of multi-parameter assessment of the relative position and orientation of the femoral and tibial components and overall limb alignment, assessed by the Perth CT protocol 3 months after surgery (Group B).

The secondary endpoint of this study is:

3. Knee function, quality of life and pain assessed 6 months after surgery (Group B).

The study objectives are:

1. Repeatability of the cutting guide position will be no worse than that obtained for manual instruments used for total knee replacement (Group A).

2. Participants will have higher knee function scores and increased quality of life as compared to pre-operative state and equal or better as compared to other surgical techniques using historical controls (Group B)

The objectives of the Extension Study are:

1. The primary objective is to determine the clinical and radiographic outcomes at 12 months, 2 years and 5 years post surgery, in patients receiving a Triathlon Custom Fit Knee featuring Stryker ShapeMatch.
2. The secondary objective is to determine the revision rate (yearly cumulative percent revision), device-related adverse events and reoperation rates.

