#### **5.0 LENGTH OF STUDY AND PATIENT PARTICIPATION**

The enrolment period for Group A is expected to be 3 months or until the required sample size is reached. For Group B, individual study participants will be seen for at least 6 months after surgery. The enrolment period is expected to be 6 months. Therefore it is anticipated that the entire study will take approximately 1.5 years to complete.

At the completion of the 6 month follow-up visit patients will receive an invite to continue participation in the study via enrollment into the Extension Study. Patients

will be required to give informed consent and will need to meet the Extension study inclusion and exclusion criteria (see sections 6.3 and 6.4).

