### **6.2 Exclusion Criteria**

- The patient has a history of total, unicompartmental reconstruction or fusion of the affected joint.
- Patient has had a high tibial osteotomy or femoral osteotomy.
- The patient is morbidly obese ( $BMI \geq 40$ ).
- The patient has a deformity which will require the use of stems, wedges or augments in conjunction with the Triathlon Total Knee System.
- The patient has a varus/valgus malalignment  $\geq 15^\circ$  (relative to mechanical axis).
- The patient has a fixed flexion deformity  $\geq 15^\circ$ .

- The patient has a neuromuscular or neurosensory deficiency, which would limit the ability to assess the performance of the device.
- The patient has a systemic or metabolic disorder leading to progressive bone deterioration.
- The patient is immunologically suppressed or receiving steroids in excess of normal physiological requirements.
- Patient has a cognitive impairment, an intellectual disability or a mental illness.
- The patient is pregnant.
- The patient has metal hardware present in the region of the hip, knee or ankle (as this is known to create geometrical distortion in the region of the implant).
- The patient has any known contraindications for undergoing assessment by MRI (e.g. ferrous implants, metallic clips, magnetically activated implanted devices such as cardiac pacemakers, etc).

**6.3 Extension Study: Inclusion Criteria (applicable to patients electing to continue participation in the Extension study).**

- Patient was enrolled in TriShapeMatch-10 study and completed 3 month follow-up visit.
- Patient is willing and able to give informed consent to participate in the study.
- Patient is willing and able to comply with the specified clinical and radiographic evaluations.

**6.4 Extension Study: Exclusion Criteria (applicable to patients electing to continue participation in the Extension study).**

- Patient no longer has the Triathlon Custom Fit Knee featuring Stryker ShapeMatch *in situ*, including patients that have had revision surgery.
- Patient has a cognitive impairment, an intellectual disability or a mental illness.
- Patient no longer resides in a geographical location that would reasonably permit clinic visits at protocol specified intervals.

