**VAS:** A Visual Analogue Scale (VAS) is a measurement instrument that tries to measure a characteristic or attitude that is believed to range across a continuum of values and cannot easily be directly measured. For example, the amount of pain that a patient feels ranges across a continuum from none to an extreme amount of pain. From the patient's perspective this spectrum appears continuous - their pain does not take discrete jumps, as a categorization of none, mild, moderate and severe (Wewers et al, 1990).

**FJS-12:** The Forgotten Joint Score is a newly-developed twelve-item, self-reported assessment of how aware recipients of hip and knee joint replacement are of their joint in everyday life (Behrend et al, 2012).

**Medical History Review:** For participants in the extension study, details of any significant medical events from time of surgery to 12 month visit will be recorded to ensure no adverse events have occurred between termination from Group B study and re-enrolment into Extension study.

All information on general medical, operative and device related complications will be documented and tabulated on case report forms (CRF).

All information on complications (date of occurrence, description, severity, related to study device, treatment and resolution) will be recorded at the time of occurrence.

All information on protocol deviations including the type of deviation (informed consent, inclusion/exclusion criteria, treatment, tests not performed and follow-up) will be recorded at the time of occurrence.

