## **12.2 Data Capture and Analysis**

All data will be recorded on 2-part NCR paper Case Report Forms (CRFs). The surgeon will complete and sign forms at the time of completion. Original CRFs will be collected by Stryker for data entry. Copies will remain at the investigator site. Archiving will be undertaken in accordance with ICH/GCP guidelines (Appendix 6).

Any unclear or ambiguous data will be queried and all cleaned data will be entered into a database for tracing purposes.

The primary outcome data gathered from Group A will be assessed using a repeated-measures analysis (Hopkins, 2009) to determine the mean and standard error of measurement between successive pairs of trials. Multiple surgeons gathering repeated measures on individual patients will be pooled to take into account varying knee anatomies and intra-observer variation.

The data from Group B and the Extension Study will be summarised and descriptive statistics will be utilised for analysis of the primary and secondary outcomes. The mean, median, standard deviation, minimum and maximum will be presented for quantitative variables. Statistical tests will be employed as deemed appropriate by a biostatistician. A significance level of 0.05 will be used for comparative tests.

Adverse events will be tabulated separately and reviewed for any commonalities.

Revision surgery data from the Extension Study will be compared to the revision rates reported in the National Joint Registry Report at 12 months, 2 years and 5 years. A cost benefit analysis will be undertaken with the use of data from the Australian Government Hospital Casemix Protocol Annual Report.

A formal interim analysis will take place following completion of each Group A and Group B sub-studies. Additionally, formal interim analyses will take place following all

participants' completion of the 12 month visit, again following completion of all participants' 2 year visit and final analysis will take place following completion of all participants' 5 year follow-up visits.

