### **17.2 Withdrawal from Study**

Participants will be advised that they may voluntarily withdraw from the study at anytime, for any reason and they are not obligated to reveal the reason to the Investigator and it will not affect their medical care. However, in such cases, appropriate effort will be made to determine the reason for withdrawal from the study. The Investigator may request a letter from the patient noting his or her desire to withdraw from the study. All attempts to locate participants lost to follow up will also be documented.

Participants will be informed that should they withdraw from the study they should remain under the care of an appropriately experienced physician until the physician deems further follow-up unnecessary.

The following are circumstances for which a patient would be identified as not continuing their participation in the study:

- Study Completed / Terminated
- Death
- Unable to Return
- Unwilling to Return
- Concurrent Illness
- Lost to follow-up

- Re-operation of the affected knee joint, including revision of total knee replacement components
- Other

Additionally, the patient may be withdrawn by the Investigator, if he/she is unable to continue participation in the study due to some condition unrelated to this study.

A Study Completion Form will be completed for all participants who withdraw from the study.

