## **18.0 MODIFICATION OF PROTOCOL**

**No changes** to this Protocol will be permitted without the written approval of the applicable Ethics Committee.

Protocol deviation details should be recorded on a Protocol Deviation Form as soon as identified and notification will be made to the applicable Ethics Committee according to the Ethics Committee requirements.

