## **19.2 Reporting of Events**

### **Adverse Events:**

***Any adverse event that occurs at any time point from the beginning of the surgical procedure until either the patient is terminated from the study, or 30 days post-completion, should be recorded as follows:***

All information on general medical, operative and device related complications (adverse events) will be documented on case report forms (CRFs). Information should include date of occurrence, description, severity, relationship to study device, treatment and date of resolution.

The investigator must determine if the event is related to the device. Any adverse event in a study patient must be monitored until the event is resolved or considered non-clinically significant by the Investigator.

**Expected Events:** Should be reported to the sponsor soon as possible, but not later than ten working days after the Investigator first learns of the effect.

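### The Extension Study's revision rate leaves out knees revised before entry but is compared with registry rates, so the comparison can only be biased in the device's favour

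*Combined protocol and SAP*

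**What the plan says.** The Extension Study's secondary objective (Section 3.0) is to "determine the revision rate (yearly cumulative percent revision), device-related adverse events and reoperation rates". The primary Extension objective in the same section sets its time points by years after surgery, and the Visit Windows text in Section 1.0 takes the surgery date as baseline.

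Four provisions decide which knees and events reach that rate:

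- **Entry time (5.0):** "At the completion of the 6 month follow-up visit patients will receive an invite to continue participation".
- **Eligibility (6.4):** patients without the study knee in place are excluded, "including patients that have had revision surgery".
- **Withdrawal (17.2):** reasons for not continuing include "Re-operation of the affected knee joint, including revision of total knee replacement components".
- **Event recording (19.2):** the adverse-event window runs from the start of surgery "until either the patient is terminated from the study, or 30 days post-completion, should be recorded as follows".

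Section 12.2 then sets the benchmark: "Revision surgery data from the Extension Study will be compared to the revision rates reported in the National Joint Registry Report at 12 months", followed by 2 years and 5 years. Its paragraph on descriptive statistics names Group B and the Extension Study as two data sources; the registry sentence names only the Extension. Adverse events are tabulated separately.

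The Medical History Review in Section 11.0 looks back to surgery, but only for Extension participants. Its purpose is to check for events "between termination from Group B study and re-enrolment into Extension study".

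**The concern.** A cumulative revision rate counted from surgery must include the knees that fail early. Here those knees are removed by an eligibility rule applied some months after surgery, while the comparator is a registry rate that presumably counts them. They leave both numerator and denominator, and the look-back in Section 11.0 cannot recover them because a barred patient never reaches it.

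Revision rate is one of three components of the Extension's secondary objective, and the registry is its only stated external benchmark. A favourable comparison could arise partly because early failures were not allowed in.

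Two recording rules may widen the gap. If completion in Section 19.2 means completion of Group B, recording for a patient not yet re-enrolled ends at about month 7. A revision after that, but before entry, would bar the patient and need not be recorded. Also, because any re-operation of the knee is listed in Section 17.2 as ending participation, a later revision of a knee first re-operated for another reason can be lost.

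**Working it through.** The plan states no expected or registry revision rate, so there is no figure of its own to reproduce. The direction follows from algebra; the size needs assumed rates.

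**Direction.** Let *N* be the knees operated on, *k* those revised before Extension entry and *r* those revised between entry and time *t*.

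- Full cohort from surgery: (k + r)/N
- Extension only: r/(N − k)
- r/(N − k) ≤ (k + r)/N ⇔ rN ≤ (k + r)(N − k) ⇔ 0 ≤ k(N − k − r)

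The last line always holds. The rates are equal only if k = 0 or every knee is revised. Enumerating 10,390 combinations for N = 50, 87 and 100 gave no exception. Example: with N = 100, k = 1, r = 1, the full-cohort rate is 2/100 = 2.0% and the Extension-only rate is 1/99 = 1.01%.

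**Inputs for size.**

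- From the plan: at most 100 Extension knees (4.0); invitation after the 6-month visit (5.0); comparisons at 12 months, 2 years and 5 years (12.2).
- Assumed: cumulative revision at 1 and 5 years of 1%/3%, 1.5%/4%, 2%/5% or 1%/5%; constant hazard h₁ in year 1 and h₂ in years 2–5; registry rates counted from primary surgery.

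**Formulas.** With H(t) the cumulative hazard and t₀ the entry time:

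- True rate: F(t) = 1 − exp(−H(t))
- Extension-only rate: 1 − exp(−(H(t) − H(t₀)))
- Understatement: 1 − (Extension-only rate)/F(t)
- Expected revisions left out per 100 knees: 100·F(t₀)
- Chance that at least one of 100 is left out: 1 − (1 − F(t₀))¹⁰⁰

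**Worked case, 1%/3%, entry at 6 months.** h₁ = −ln(0.99) = 0.01005. h₂ = (−ln(0.97) − 0.01005)/4 = 0.00510. H(0.5) = 0.00503.

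| Time | True rate | Extension only | Understatement |
|---|---|---|---|
| 12 months | 1.00% | 0.50% | 49.9% |
| 2 years | 1.50% | 1.01% | 33.0% |
| 5 years | 3.00% | 2.51% | 16.3% |

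**Range over the four rate pairs.**

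| | Entry at 6 months | Entry at 12 months |
|---|---|---|
| Left out per 100 knees | 0.5–1.0 | 1.0–2.0 |
| Chance at least one left out | 39–64% | 63–87% |
| Understatement, 12 months | 49.7–49.9% | 100% |
| Understatement, 2 years | 24.5–35.8% | 49.1–71.9% |
| Understatement, 5 years | 9.6–19.3% | 19.2–38.8% |

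The plan does not say that entry occurs at the 12-month visit; that column is the worst case.

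**Sensitivity.** The 50% at 12 months reflects the constant first-year hazard. If 30% to 70% of that hazard falls in the first 6 months, understatement with entry at 6 months is 29.8–69.9% at 12 months, 14.7–50.2% at 2 years and 5.7–27.1% at 5 years.

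**Recording gap.** For a patient not re-enrolled before month 12, revisions after month 7 are 100·(F(1) − F(7/12)) = 0.42 to 0.83 per 100 knees, about 41–42% of first-year revisions. With the 30–70% variation this becomes about 0.25 to 1.2.

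**Sampling error for scale.** Exact 95% intervals (Clopper-Pearson): 0/100, 0–3.62%; 1/100, 0.03–5.45%; 2/100, 0.24–7.04%.

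**The case against.** The strongest reply is that the plan can be read more generously. The Extension is presented as continued follow-up of Group B, the time points are after surgery, and early revisions would be on Group B adverse-event and Study Completion Forms. An analyst might therefore count them. That is possible, but Section 12.2 does not say so: it names the Extension alone as the source for the registry comparison, and no other section links Group B events to it.

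Several limits do stand:

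- If no knee is revised before entry, the exclusion has no effect. On the assumed rates with entry at 6 months, that has a 36–61% chance (100% minus 39–64%).
- The registry report is not in the documents. That its clock starts at surgery and includes early revisions is inferred from the cumulative measure.
- The large relative percentages describe about one knee or fewer per 100 with entry at 6 months, and sampling error is wider.
- Section 19.2 does not say whether completion means Group B or the whole study, so the month-7 cut-off is one reading. The serious-event rules have the same end point and do not settle it.
- The loss of revisions after another re-operation is a separate withdrawal matter, not caused by Section 6.4, and has not been sized.
- Re-consent and the residence criterion add selection of unknown direction.
- The study is a case series with no success threshold for this comparison, and its primary endpoints are untouched.

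These points limit the consequence. They do not restore the missing early revisions or change the sign of the bias.

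**Conclusion.** The concern holds. Followed as written, Sections 5.0, 6.4 and 12.2 give a revision rate conditional on being unrevised at Extension entry and compare it with a rate that, by inference, carries no such condition. The sign is certain: the exclusion lowers the study rate or leaves it unchanged. The size rests wholly on the assumed rates and on when patients enter. With entry at 6 months it is modest in absolute terms but a material fraction of the reported rate, most of all at 12 months. Only if entry is at the 12-month visit is the 12-month rate near zero by construction.

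This should be fixed: the error favours the device, a larger sample would not reduce it, and removing it is cheap. Early revisions remain visible in Group B adverse-event reporting; the fault lies in the registry benchmark.

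**What to change.** In Section 12.2, define the revision analysis as cumulative percent revision in **all Group B knees, with time zero at the index surgery**, by Kaplan-Meier with 95% confidence intervals at 12 months, 2 years and 5 years. Specify that:

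- revisions on Group B adverse-event forms and Study Completion Forms count as events;
- revision found at Extension invitation or re-consent is recorded as the reason for ineligibility, with its date, and counts as an event rather than censoring the knee at its last Group B contact;
- for knees leaving under Section 17.2 after a non-revision re-operation, the type and date are recorded and the plan says how later revision status will be obtained, or reports how many have unknown status;
- other non-consenters are censored at the last contact at which revision status was known.

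Section 19.2 should also say which completion ends event recording for a patient awaiting re-enrolment.

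If only Extension participants can be analysed, use delayed-entry (left-truncated) risk sets, label the result as conditional on being unrevised at entry, and drop the 12-month registry comparison.

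The cost is a revision status and date field on the Extension invitation record, a re-operation type and date on the Study Completion Form, and an amendment: Section 18.0 says that no changes "to this Protocol will be permitted without the written approval of the applicable Ethics Committee". Rewording Section 12.2 alone would not recover revisions that were never recorded. The sponsor should also check that the original consent covers collecting revision status from patients who do not sign the second consent in Section 10.0. No new visits or imaging are needed. The reported revision rate may become slightly less favourable.

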## 2.0 INTRODUCTION

Total knee replacement has evolved to a point where implant design combined with instrumentation and surgeon skill results in excellent implant survival. Over 30,000 total knee replacement procedures are performed each year in Australia and are used to treat a range of conditions including osteoarthritis, rheumatoid arthritis, avascular necrosis and secondary arthritis resulting from trauma.

Current surgical techniques make use of generic, re-usable instrumentation, consisting of intra- and/or extra-medullary rods on the femur and tibia to determine alignment in relation to anatomical landmarks, combined with bone resection guides which ultimately determine position and orientation of the definitive implant components.

[figure not shown]
Traditionally, the goal of total knee replacement has been to position the components such that the post-operative alignment goal is a straight limb, or a mechanical axis of 0° (Insall & Scott, 2001). The mechanical axis is defined by lines joining the centre of the femoral head, centre of the knee joint and the centre of the ankle. Despite the best efforts of the surgeon, the resulting limb alignment varies away from 0° by a small amount (typically  $\pm 3^\circ$  in 80% of cases).

More recently, the use of computer navigation systems has been introduced to surgical practice with the aim of improving the ability to obtain post-operative limb alignment as close as possible to 0° (Chauhan et al, 2004).

[figure not shown]
Whilst achievement of neutral limb alignment has been considered desirable from an engineering point-of-view – to maximize implant longevity through minimizing the deleterious effects of polyethylene insert wear and particle-induced osteolysis and implant loosening – patient satisfaction of total knee replacement has not always been ideal. Despite surgery being performed technically correct by surgeons, up to 1 in 5 patients express dissatisfaction in the functional result (Bourne et al, 2009). Patient expectations after surgery are also increasing due in part to the adoption of more active lifestyles amongst total knee replacement recipients where return to function can be of primary importance.

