### **6.1 Inclusion Criteria**

- The patient is a male or non-pregnant female between the ages of 50-90.
- The patient requires a primary total knee replacement and is indicated for computer-assisted surgery.
- The patient has a primary diagnosis of osteoarthritis (OA).
- The patient has intact collateral ligaments.
- The patient is able to undergo MRI scanning of the affected limb.
- The patient has signed the study specific, HREC-approved, Informed Consent document.
- The patient is willing and able to comply with the specified pre-operative and post-operative clinical and radiographic evaluations.

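### Section 12.2 does not say which registry revision rates are the comparator, or how case mix is handled for a selected osteoarthritis cohort

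*Combined protocol and SAP*

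**What the plan says.** Section 12.2 gives the whole plan for revision, for three time points (12 months, 2 years, 5 years): "Revision surgery data from the Extension Study will be compared to the revision rates reported in the National Joint Registry Report". No diagnosis, age, sex or prosthesis stratum is named, and no matching, standardisation or interval. On method it adds only "Statistical tests will be employed as deemed appropriate by a biostatistician" and "A significance level of 0.05 will be used for comparative tests". Section 3.0 makes revision part of the Extension Study's objectives: "The secondary objective is to determine the revision rate (yearly cumulative percent revision), device-related adverse events and reoperation rates".

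The cohort is narrow. Section 6.1 requires a primary diagnosis of osteoarthritis, age 50-90 and an indication for computer-assisted surgery. Section 6.2 excludes BMI of 40 or more, previous osteotomy, malalignment or fixed flexion of 15° or more, immune suppression and disorders causing progressive bone deterioration. It also lists: "The patient has a deformity which will require the use of stems, wedges or augments". By contrast, section 2.0 says that knee replacement in Australia treats "osteoarthritis, rheumatoid arthritis, avascular necrosis and secondary arthritis resulting from trauma".

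Three further provisions decide which revisions are counted. Section 5.0 issues the extension invitation after the 6-month visit. Section 6.4 bars patients whose knee has already been revised. Section 17.2 lists re-operation or revision among the reasons for not continuing. Section 4.0 caps the Extension Study at 100 cases.

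**The concern.** There is no concurrent control, so the registry rate carries the whole comparison. If it describes all knee replacements and the trial describes a selected osteoarthritis group, a difference in revision may reflect who was admitted rather than how the bone was cut. The comparison as written cannot tell these apart.

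Leaving the comparator open has a second cost. Analyses are planned after the 12-month and 2-year visits as well as at 5 years, so the registry figure could be chosen once trial results are known. At stake is how a secondary objective of the Extension Study is interpreted; the Group A and Group B endpoints are unaffected.

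**Working it through.** **1. The plan's own figure.** The documents' only power calculation is for the Knee Society Score (section 12.1): 15 points, SD 35, 80% power, independent-groups t-test. At two-sided 0.05 the t-test solution is 86.44, rounded up to 87 per group, as stated. Then 87/(1 − 0.13) = 100, so the total of 100 implies about 13% dropout. This does not bear on revision, for which no expected rate, margin or sample size is given.

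**2. Effect of case mix.** Let R be the all-comer registry rate, r the rate among registry patients the trial would admit, s the share it would exclude, and k the excluded patients' relative revision risk. Then R = (1 − s)r + s·k·r, so

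r/R = 1/(1 − s + s·k).

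The documents give neither s nor k, so both are assumed over a range:

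| s | k = 0.8 | k = 1.25 | k = 1.5 | k = 2.0 |
|---|---|---|---|---|
| 5% | 1.010 | 0.988 | 0.976 | 0.952 |
| 10% | 1.020 | 0.976 | 0.952 | 0.909 |
| 20% | 1.042 | 0.952 | 0.909 | 0.833 |
| 30% | 1.064 | 0.930 | 0.870 | 0.769 |

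With k above 1, the like-for-like rate is about 0.99 to 0.77 of the all-comer rate. With k = 0.8 it is higher than the all-comer rate, and the tilt runs against the device.

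**3. In revisions.** Assume R = 4% at 5 years and 100 cases, so 4.0 revisions are expected.
- s = 10%, k = 1.5: 4.0/1.05 = 3.8, a shift of 0.2.
- s = 20%, k = 2: 4.0/1.20 = 3.3, a shift of 0.7.
- s = 30%, k = 2: 4.0 × 0.769 = 3.1, a shift of 0.9.

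For a device no better than the registry, the binomial chance of seeing fewer than 4 revisions in 100 is 43% at a true rate of 4%. It is 63% at 0.77 × 4% = 3.08%.

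**4. Against sampling error.** The exact (Clopper-Pearson) 95% CI for 4/100 is 1.1% to 9.9%, several times wider than any shift in step 3.

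**5. Entry condition.** Assume the registry counts from surgery and that a fraction f of patients are revised before extension entry. The extension cohort's expected 5-year rate is then (R − f)/(1 − f). With R = 4%:
- f = 0.5%: 3.5/99.5 = 3.52%, ratio 0.88.
- f = 1.0%: 3.0/99.0 = 3.03%, ratio 0.76.

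On these assumed values, section 6.4 alone matches or exceeds most of the case-mix table. Matching case mix while ignoring entry would leave the comparison uneven.

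**The case against.** The strongest reply is that the plan is silent rather than wrong. Section 12.2 does not say that all-comer rates will be used, does not rule out an osteoarthritis or prosthesis-specific figure, and leaves method to a biostatistician. Section 2.0 is background: it gives no diagnosis shares and does not describe the registry report. All of this stands, and it limits the point to an unspecified comparator.

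A reader might go further and infer that the cohort is known to be lower-risk, so that the comparison is biased towards the sponsor's device. The documents do not support that as fact. Nowhere do they say that the excluded patients are revised more often, and they give no registry rates or case mix. The requirement for a computer-assisted indication is a further selection whose direction is unknown. The exclusions for complex deformity, bone deterioration and immune suppression make a favourable tilt plausible, but no more than that.

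It is also fair to say that the effect is small beside the sampling error and that this is a secondary objective of a self-described case series, with randomised trials envisaged later. That sets the priority of the point. It does not remove the case for naming the comparator in advance, since an interval around the trial's rate does not correct a mismatched reference.

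**Conclusion.** The point holds as a gap in specification. Section 12.2 does not state which registry stratum will be used or how case mix will be handled, and the cohort is plainly narrower than the national population that the protocol describes. If an all-comer rate were used, selection and device effect could not be separated.

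The direction is probably favourable to the device. Its size, a like-for-like rate of roughly 0.77-0.99 of the all-comer rate, rests on an assumed excluded share of 5-30% and an assumed relative risk of 1.25-2, and it reverses if that risk is below 1. At an assumed 4% over 5 years, this is less than one revision per 100 cases. Exclusion of knees revised before entry may matter as much (ratio 0.88-0.76, also on assumed figures) and belongs in the same correction. This is a low-cost improvement, not a threat to the study's main conclusions.

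**What to change.** Amend section 12.2 before any revision data are compared:

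1. Name the closest published registry stratum: primary total knee replacement for osteoarthritis, with age band, sex and prosthesis where reported. State which report edition will be used.
2. Apply the stratum rates to the trial's age and sex mix and to each patient's actual follow-up, ending at revision, death, withdrawal or last contact. The sum is the expected number of revisions.
3. Report observed versus expected revisions with an exact 95% CI at 12 months, 2 years and 5 years.
4. Count revisions from the date of surgery in all Group B patients, including those turned away under section 6.4. Otherwise, condition the registry rates on being unrevised at extension entry and start follow-up there. State how revision is ascertained after a re-operation that ends participation under section 17.2.
5. List the exclusions that cannot be matched, such as BMI and deformity, record any unpublished stratum as a limitation, and label the comparison descriptive.

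Date of birth, sex and diagnosis are already collected (sections 7.0 and 11.0). The cost is revised wording and a short calculation. Counting from surgery also means recording revision status and date for Group B patients who do not enter the extension. The documents do not show which strata the registry publishes, so that must be checked. The downside for the sponsor is a possibly less favourable comparator.
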